8.0 Hematologic Toxicities	
8.1 Autoimmune hemolytic anemia	
Definition: A condition in which RBCs are destroyed and removed from the blood stream before their normal lifespan is over. Symptoms include weakness, paleness, jaundice, dark-colored urine, fever, inability to do physical activity, and heart murmur.	
Diagnostic work-up	
History and physical examination (with special consideration of history of new drugs and insect, spider, or snake bites)	
Blood chemistry, CBC with evidence of anemia, macrocytosis, evidence of hemolysis on peripheral smear; LDH, haptoglobin, bilirubin, reticulocyte count, free Hgb DIC panel, which could include PTNIR infectious causes	
Autoimmune serology	
Paroxysmal nocturnal hemoglobinuria screening	
Direct and indirect bilirubin; LDH; direct agglutinin test; and if no obvious cause, bone marrow analysis, cytogenetic analysis to evaluate for myelodysplastic syndromes	
Evaluation for viral/bacterial (mycoplasma, etc) causes of hemolysis	
studies Protein electrophoresis, cryoglobulin analysis	
Work-up for bone marrow failure syndrome if refractory, including B12, folate, copper, parvovirus, FE, thyroid, infection	
Glucose-6-phosphate dehydrogenase	
Evaluation of common drug causes (ribavirin, rifampin, dapsone, interferon, cephalosporins, penicillins, NSAIDs, quinine/quinidine, fludarabine, ciprofloxacin, lorazepam, diclofenac, etc)	
Assessment of methemoglobinemia	
Grading	Management
G1: Hgb < LLN to 10.0 g/dL; < LLN to 6.2 mmol/L; < LLN to 100 g/L	Continue ICPi with close clinical follow-up and laboratory evaluation
G2: Hgb < 10.0 to 8.0 g/dL; < 6.2 to 4.9 mmol/L; < 100 to 80 g/L	Hold ICPi and strongly consider permanent discontinuation Administer 0.5-1 mg/kg/d prednisone equivalents
G3: Hgb < 8.0 g/dL; < 4.9 mmol/L; < 80 g/L; transfusion indicated	Permanently discontinue ICPi Should use clinical judgment and consider admitting the patient Hematology consult Prednisone 1-2 mg/kg/d (oral or IV depending on symptoms/speed of development) If worsening or no improvement, 1-2 mg/kg/d prednisone equivalents and permanently discontinue ICPi treatment

8.0 Hematologic Toxicities	
	Consider RBC transfusion per existing guidelines; do not transfuse more than the minimum number of RBC units necessary to relieve symptoms of anemia or to return a patient to a safe Hgb range (7-8 g/dL in stable, noncardiac inpatients) Should offer patients supplementation with folic acid 1 mg once daily
G4: Life-threatening consequences, urgent intervention indicated	Permanently discontinue ICPi Admit patient Hematology consult IV prednisone corticosteroids 1-2 mg/kg/d If no improvement or if worsening while on corticosteroids or severe symptoms on presentation, initiate other immunosuppressive drugs, such as rituximab, IVIG, cyclosporin A, and mycophenolate mofetil RBC transfusion per existing guidelines; discuss with blood bank team prior to transfusions that a patient with possible ICPi serious AE is in house.
Additional considerations: Monitor Hgb levels on a weekly basis until the corticosteroid tapering process is complete; thereafter, less-frequent testing is needed	
8.2 Acquired TTP	
Definition: A disorder characterized by the presence of microangiopathic hemolytic anemia, thrombocytopenic purpura, fever, renal abnormalities, and neurologic abnormalities, such as seizures, hemiplegia, and visual disturbances. It is an acute or subacute condition.	

Diagnostic work-up
 
History with specific questions related to drug exposure (eg, chemotherapy, sirolimus, tacrolimus, opana ER antibiotics, quinine) Physical examination, peripheral smear ADAMTS13 activity level and inhibitor titer
 
LDH, haptoglobin, reticulocyte count, bilirubin, urinalysis to rule out other causes
 
PT, activated PTT, fibrinogen
 
Blood group and antibody screen, direct antiglobulin test, CMV serology
 
Consider CT/MRI brain, echocardiogram, ECG
 
Viral studies
 
Note: This disorder is usually associated with a severe drop in platelets and hemolysis/anemia precipitously
	

8.0 Hematologic Toxicities	
Grading	Management
All grades	
The first step in the management of TTP is a high index of suspicion for the diagnosis and timely recognition; hematology consult should immediately be called, as delay in identification is associated with increased mortality/morbidity.
 
Initially, the patient should be stabilized and any critical organ dysfunction stabilized

G1: Evidence of RBC destruction (schistocytosis) without anemia, renal insufficiency, or thrombocytopenia clinically G2: Evidence of RBC destruction (schistocytosis) without clinical consequence with G2 anemia and thrombocytopenia	
Hold ICPi and discuss resumption with patient only after taking into account the risks and benefits, noting that there are currently no data to recommend restarting ICPi therapy
 
Hematology consult
 
Administer 0.5-1 mg/kg/d prednisone

G3: Laboratory findings with clinical consequences (G3 thrombocytopenia, anemia, renal insufficiency > 2) G4: Life-threatening consequences (eg, CNS hemorrhage or thrombosis/embolism or renal failure)	
Hold ICPi and discuss resumption with patient only after taking into account the risks and benefits, noting that there are currently no data to recommend restarting ICPi therapy
 
Hematology consult
 
In conjunction with hematology, initiate PEX according to existing guidelines with further PEX dependent on clinical progress
 
Administer methylprednisolone 1 g IV daily for 3 days, with the first dose typically administered immediately after the first PEX
 
May offer rituximab

8.3 Hemolytic uremic syndrome	

Definition: A disorder characterized by a form of thrombotic microangiopathy with renal failure, hemolytic anemia, and severe thrombocytopenia. Signs and symptoms of hemolytic uremic syndrome can include:
 
Bloody diarrhea
 
Decreased urination or blood in the urine
 
Abdominal pain, vomiting, and occasionally fever
 
Pallor
 
Small, unexplained bruises or bleeding from the nose and mouth
 
Fatigue and irritability
 
Confusion or seizures
 
High blood pressure
 
Swelling of the face, hands, feet, or entire body
	

Diagnostic work-up
 
History and physical examination (special consideration for new history of high-risk drugs, hypertension, or cardiac causes)
 
CBC with indices
 
Blood smear morphology. Note that the presence of schistocytes on smear is critical for diagnosis.
 
Serum creatinine
	

8.0 Hematologic Toxicities	
ADAMTS13 (to rule out TTP) Homocysteine/methylmalonic acid Complement testing C3, C4, CH50 (complement inhibitory antibodies for suspected familial) Evaluate reticulocyte count and mean corpuscular volume Evaluation of infectious cause, including screening for EBV, CMV, HHV6 Evaluation for nutritional causes of macrocytosis (B12 and folate) Pancreatic enzymes Evaluation for diarrheal causes, shiga toxin, Escherichia coli 0157, etc Direct antibody test (Coombs test), haptoglobin, LDH, and other etiologies of anemia Evaluation for common drugs causing hemolysis (tacrolimus, cyclosporine, sirolimus, etc) Evaluation for concurrent confusion	
Grading	Management
G1-2: Evidence of RBC destruction (schistocytosis) without clinical consequences of anemia, thrombocytopenia Grade 2 G3: Laboratory findings with clinical consequences (eg, renal insufficiency, petechiae) G4: Life-threatening consequences (eg, CNS thrombosis/ embolism or renal failure)	Continue ICPi with close clinical follow-up and laboratory evaluation Supportive care Permanently discontinue ICPi Begin therapy with eculizumab therapy 900 mg weekly for four doses, 1,200 mg week 5, then 1,200 mg every 2 weeks Red blood transfusion according to existing guidelines
8.4 Aplastic anemia	Definition: Condition in which the body stops producing enough new blood cells
Diagnostic work-up History and physical examination (close attention to medications, exposure to radiation, toxins, recent viral infections) CBC, smear, reticulocyte count Viral studies, including CMV, HHV6, EBV, parvovirus Nutritional assessments including B12, folate, iron, copper, ceruloplasmin, vitamin D Serum LDH, renal function Work-up for infectious causes Identify marrow hypo/aplasia Bone marrow biopsy and aspirate analysis Peripheral blood analysis, including neutrophil count, proportion of GPI-negative cells by flow for PNH Flow cytometry to evaluate loss of GPI-anchored proteins Type and screen patient for transfusions and notify blood bank that all transfusions need to	
Grading	Management
G1: Nonsevere, < 0.5 polymorphonuclear cells $\times 10^9/L$ hypocellular marrow, with marrow cellularity < 25%, peripheral platelet count 20,000, reticulocyte count < 20,000	Hold ICPi and provide growth factor support and close clinical follow-up, and laboratory evaluation Supportive transfusions as per local guidelines

8.0 Hematologic Toxicities	
G2: Severe, hypocellular marrow < 25% and two of the following: ANC < 500, peripheral platelet < 20,000, and reticulocyte < 20,000	Hold ICPI and provide growth factor support and close clinical laboratory evaluations daily Administer ATG + cyclosporine; HLA typing and evaluation for bone marrow transplantation if patient is candidate; all blood products should be irradiated and filtered Supportive care with granulocyte colony-stimulating factor may be added in addition
G3-4: Very severe, ANC > 200, platelet count > 20,000, reticulocyte count > 20,000, plus hypocellular marrow > 25%	Hold ICPI and monitor weekly for improvement; if not resolved, discontinue treatment until AE has reverted to G1 Hematology consult, growth factor support Horse ATG plus cyclosporine If no response, repeat immunosuppression with rabbit ATG plus cyclosporine, cyclophosphamide For refractory patients, consider eltrombopag plus supportive care

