10.1 Inclusion Criteria

1. Age \geq 18 years
2. Histologically or cytologically confirmed previously untreated NSCLC. If a diagnostic biopsy is available, a pre-treatment biopsy is not required. Patients with a suspected lung cancer are eligible, but pathology must be confirmed prior to initiating treatment on study. Neuroendocrine carcinomas (e.g. SCLC, large cell neuroendocrine carcinoma, atypical carcinoid, carcinoid) are not eligible. Non-small cell carcinomas with neuroendocrine differentiation are eligible.
3. Patients with stage I-IIIA disease and IIIB (T3N2 only, and N2 single station), according to AJCC 8th edition, are eligible for arm A of the study. Patients with stage III, N2 single station, must not have more than one mediastinal lymph node station involved by tumor.
4. All patients must have lymph node evaluation of contralateral stations 2 and/or 4 to exclude N3 disease.
5. The patient must be a suitable candidate for surgery, in the opinion of the treating physician.
6. Predicted FEV1 \geq 50%
7. Predicted DLCO \geq 50%
8. Signed and dated written informed consent must be provided by the patient prior to admission to the study in accordance with ICH-GCP guidelines and to the local

legislation

9. ECOG performance status score 0-1
10. Patients must have organ and marrow function as defined below:
 - a. Absolute neutrophil count (ANC): $\geq 1.5 \times 10^9 / \text{L}$
 - b. Hemoglobin: $\geq 9.0 \text{ g/dL}$
 - c. Platelets $\geq 100 \times 10^9 / \text{L}$
 - d. Total bilirubin: $\leq 1.5 \times \text{ULN}$ (except subjects with Gilbert Syndrome, who can have total bilirubin $< 3.0 \text{ mg/dL}$)
 - e. AST and ALT: $\leq 3 \times \text{ULN}$
 - f. Creatinine: $\leq 1.5 \times \text{ULN}$ or Calculated creatinine clearance¹: $\geq 50 \text{ mL/min}$ or 24-hour urine creatinine clearance: $\geq 50 \text{ mL/min}$

¹*Cockcroft-Gault formula for creatinine clearance calculation:*

Female CrCl = $(140 - \text{age in years}) \times \text{weight in kg} \times 0.85$

72 \times \text{serum creatinine in mg/dL}

Male CrCl = $(140 - \text{age in years}) \times \text{weight in kg} \times 1.00$

72 \times \text{serum creatinine in mg/dL}

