14.7.2 Immune-related Adverse Events

Immune-related AEs are specific to immunotherapies and vary by organ system. Immune-related AEs are important identified risks for M7824. The recommendations for irAE management, in accordance with the joint American Society of Clinical Oncology (ASCO) Clinical Practice Guidelines (Brahmer, 2018) and National Comprehensive Cancer Network (NCCN) (NCCN Guidelines®), are listed in Appendix 1. These irAEs include: pneumonitis, colitis, hepatitis, endocrinopathies (including hypophysitis, thyroid disorders, type 1 diabetes mellitus), and nephritis.

General management by NCI-CTCAE v5.0 grading, as per ASCO, is listed below:

- Grade 1: study treatment should be continued with close monitoring, with the exception of some neurologic, hematologic, and cardiac toxicities.
- Grade 2: study treatment may be suspended for most Grade 2 toxicities, with consideration of resuming when symptoms revert to Grade 1 or less. Corticosteroids may be administered (initial dose of 0.5 to 1 mg/kg/d of prednisone or equivalent).

- Grade 3: study treatment is generally suspended and the high-dose corticosteroids (prednisone 1 to 2 mg/kg/d or methylprednisolone 1 to 2 mg/kg/d) treatment should be initiated. Corticosteroids should be tapered over the course of at least 4 to 6 weeks. Some refractory cases may require infliximab or other immunosuppressive therapy.
- Grade 4: in general, permanent discontinuation of study treatment is recommended, with the exception of endocrinopathies that have been controlled by hormone replacement.

For organ/system specific management guidelines, review ASCO guideline tables in Appendix 1.

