22 STATISTICAL CONSIDERATIONS

This is an open label phase II study with a modular design. Currently, eligible patients will be accrued to the M7824 monotherapy arm (Arm A). The primary objective is to evaluate the rate of MPR, rather than hypothesis testing with pre-specified null and alternative MPR rates. There will be no interim futility nor efficacy monitoring. The primary efficacy endpoint of the study is MPR evaluated in resected tumor tissues following neoadjuvant therapy and defined as $\leq 10\%$ viable tumor cells in the resected specimen using the methods described by Pataer et al. (2).

Analysis of primary efficacy endpoint:

A sample size of 23 patients is proposed for each arm of the study. With an estimated accrual rate of 2-3 patients a month, the accrual period is approximately 15-24 months. We will estimate the MPR rate with a 95% credible interval (CI) assuming that the MPR rate follows a prior beta distribution (0.5, 0.5) with one patient worth of information. For example, if the M7824 monotherapy indeed has a true MPR rate of 30% and 7 patients with MPR are observed in this study, the corresponding 95% CI of the observed MPR rate would be (14.8%, 50.7%).

Furthermore, we calculated predictive probability of $\text{Prob}(p > 0.15 | \text{data and true MPR rate})$ for a variety of true MPR rates, where p is the MPR rate. As shown in the table below (**Table 3**), there will be a fairly high chance (81 – 89%) for the study to observe a MPR rate $> 15\%$ with a sample size of 23 patients if the true MPR rates are 25% and higher.

Table 3. Predictive probabilities of true MPR rates.

True MPR rate	predictive probability of $\text{Prob}(p > 0.15 \text{data and true MPR rate})$ where $a_0=0.5, b_0=0.5$
---------------	--

0.05	12%
0.10	30%
0.15	50%
0.20	67%
0.25	81%
0.30	89%

We chose to use 15% MPR rate as cutoff because a historic major pathologic responserate to neoadjuvant chemotherapy alone of 19% is observed (as described by Pataer et al.) (2). However, some patients that receive neoadjuvant chemotherapy may not receive surgery for one reason or another, and these cases will be considered treatment failure. Assuming the 19% major pathologic response rate is calculated from 80% of patients who receive surgery, a conservative estimate of the major pathologic response is 15%.

Analysis of Secondary/Exploratory Endpoints:

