8.0 Hematologic Toxicities	
8.6 Immune thrombocytopenia	
Definition: An autoimmune disorder characterized by immunologic destruction of otherwise normal platelets	
Diagnostic work-up History and physical examination (special attention for lymphocyte-depleting therapy, such as fludarabine, ATG, corticosteroids, cytotoxic therapy) Family history of autoimmunity or personal history of autoimmune disease	
History of viral illness CBC Peripheral blood smear, reticulocyte count Bone marrow evaluation only if abnormalities in the above test results and further investigation is necessary for a diagnosis Patients with newly diagnosed immune thrombocytopenia should undergo testing for HIV, hepatitis C virus, hepatitis B virus, and Helicobacter pylori Direct antigen test should be checked to rule out concurrent Evan syndrome	
Nutritional evaluation Bone marrow evaluation if other cell lines affected and concern for aplastic anemia	
Grading	Management
G1: Platelet count < 100/µL G2: Platelet count < 75/µL	Continue ICPi with close clinical follow-up and laboratory evaluation Hold ICPi but monitor for improvement; if not resolved, interrupt treatment until AE has reverted to G1 Administer prednisone 1 mg/kg/d (dosage range, 0.5-2 mg/kg/d) orally for 2-4 weeks after which time this medication should be tapered over 4-6 weeks to the lowest effective dose IVIG may be used in conjunction with corticosteroids if a more-rapid increase in platelet count is required.
G3: Platelet count < 50/µL	Hold ICPi but monitor for improvement; if not resolved, interrupt treatment until AE has reverted to G1
G4: Platelet count < 25/µL	Hematology consult Prednisone 1-2 mg/kg/d (oral or IV depending on symptoms) If worsening or no improvement, 1-2 mg/kg/d prednisone equivalents and permanently discontinue treatment IVIG used with corticosteroids when a more- rapid increase in platelet count is required If IVIG is used, the dose should initially be 1 g/kg as a one-time dose. This dosage may be repeated if necessary

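### Table A8, 8.4 and 8.6: the aplastic anemia Grade 3-4 row runs opposite to Grade 2, and the immune thrombocytopenia cut-offs are 1,000-fold below the protocol's own platelet unit

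*Combined protocol and SAP*

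**What the plan says.** Section 14.7.2 sets general management of immune-related events by CTCAE v5.0 grade and then directs the reader onward: "For organ/system specific management guidelines, review ASCO guideline tables in Appendix 1". Section 15.3 also points to Appendix 1 for suspected Grade 3 immune-related events, because many of them call for permanent discontinuation.

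Within Appendix 1, Table A8:

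- **8.4, Grade 1 (non-severe):** neutrophils below 0.5 × 10^9/L, "with marrow cellularity < 25%, peripheral platelet count 20,000, reticulocyte count < 20,000". The platelet figure carries no sign.
- **8.4, Grade 2:** "Severe, hypocellular marrow < 25% and two of the following: ANC < 500, peripheral platelet < 20,000, and reticulocyte < 20,000".
- **8.4, Grade 3-4:** "Very severe, ANC > 200, platelet count > 20,000, reticulocyte count > 20,000, plus hypocellular marrow > 25" (the last figure a percentage).
- **8.6, Grades 1 to 4:** platelets below 100, 75, 50 and 25, each per µL. The last is printed as "G4: Platelet count < 25" per µL.

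Section 10.1 sets the platelet entry limit at 100 × 10^9/L or more. Sections 11.3 and 14.7.2 and Appendix 2 all name CTCAE v5.0 for grading adverse events.

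**The concern.** A grading table has to be ordered: a worse patient should meet the same grade or a higher one. The 8.4 scale reverses direction at its top grade, and 8.6 sits in a range far below any other platelet figure in the protocol.

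What is at stake is the management step attached to the row. In 8.6 the row separates continuing with follow-up (Grade 1) from holding drug and starting corticosteroids (Grade 2), and from hematology consultation and possible permanent discontinuation (Grades 3 and 4). In 8.4 drug is held at every grade, but hematology consultation and the steps for non-response or refractory disease appear only under Grade 3-4.

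Blood counts are scheduled before doses 2 and 3, so a platelet count will be in hand at those dosing decisions. Mucosal bleeding is a listed potential risk, and patients go on to thoracic surgery. A physician who follows the table literally gets no instruction from 8.6. One who silently corrects it is applying a rule that is not written down.

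**Working it through.** No sample size, power or interval figure is involved. The check is a unit conversion plus a literal application of the printed rules.

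**8.6, units.** 1 × 10^9/L = 1,000/µL.

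- Entry limit (section 10.1): 100 × 10^9/L = 100 × 1,000 = 100,000/µL.
- Ratio to the printed Grade 1 cut-off: 100,000 / 100 = 1,000.
- A patient entering at the limit reaches printed Grade 1 with less than 100 / 100,000 = 0.1% of the entry count left (a loss of more than 99.9%), and Grade 4 with less than 25 / 100,000 = 0.025% left (a loss of more than 99.975%).
- The platelet figure in 8.4 is 20,000. Read per µL, it is 20,000 / 100 = 200 times the 8.6 Grade 1 cut-off and 20,000 / 25 = 800 times the Grade 4 cut-off.
- Applied literally, counts of 99,000, 49,000, 24,000, 20,000, 5,000 and 1,000/µL all match no row of 8.6.

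The 8.4 figures for platelets, reticulocytes and ANC print no unit, so reading them per µL is an assumption. The Grade 1 neutrophil figure supports it: 0.5 × 10^9/L = 500/µL, the same number as the Grade 2 ANC limit.

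**8.4, direction.**

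| Measure | Grade 2 | Grade 3-4 |
|---|---|---|
| Marrow cellularity | < 25% (required) | > 25% |
| ANC | < 500 | > 200 |
| Platelets | < 20,000 | > 20,000 |
| Reticulocytes | < 20,000 | > 20,000 |
| Rule | marrow plus two of three counts | all four |

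Marrow cannot be both below and above 25%, so no patient can meet both rows. A grid of 1,072,929 combinations of the four measures agrees: 44,320 points meet Grade 2, 314,496 meet Grade 3-4, and none meets both.

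Test patients, in the order ANC, platelets, reticulocytes, marrow:

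- 450; 19,000; 19,000; 20%: Grade 2.
- 50; 3,000; 3,000; 5%: still Grade 2, and not Grade 3-4.
- 1,500; 100,000; 50,000; 50% (the first two are the section 10.1 entry limits, the last two are assumed): meets every number in the Grade 3-4 row.

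**8.4, Grade 1.** Anyone with neutrophils below 500, reticulocytes below 20,000 and marrow below 25% already has the marrow condition and two of the three counts for Grade 2. As the row reads here, with no platelet sign, Grade 1 is not separated from Grade 2 either.

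**Rest of Table A8.** Hemoglobin in 8.1 and lymphocytes in 8.5 fall as the grade rises, as expected. The faults shown are in 8.4 and 8.6 only.

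**The case against.** The strongest reply is that these rows do not grade anything in the trial. CTCAE v5.0 does, and the general rules in 14.7.2 (suspension at Grades 2 and 3, discontinuation at Grade 4) and in 15.3 (Grade 4 and recurrent Grade 3 reactions) act on those grades whatever Table A8 prints. This stands. A reader might infer from 8.6 that serious platelet loss would go ungraded, or that drug would not be held at all; the documents do not support either. Nor does reporting suffer: events of special interest must be reported whatever their Table A8 grade.

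In 8.4, a patient left at Grade 2 is still held, has daily laboratory evaluation, receives immunosuppression and is assessed for transplantation. So the harm there is mis-sorted steps, not a missed hold. A reader might also fear that different sites would apply different scales, but this is a single-institution trial and further sites are only a possibility.

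CTCAE does not, however, settle the matter. The Grade 1 rule in 14.7.2 makes an exception for some hematologic toxicities. Appendix 1 has its own grading columns: the colitis table says it uses CTCAE and the skin table says it departs from it, while 8.4 and 8.6 give numbers without citing CTCAE. No sentence says which prevails.

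The other reply is that the text was damaged in conversion. Signs are corrupted elsewhere in Appendix 1, for example a dollar sign or a hash where a comparison sign belongs, and the 8.4 Grade 1 platelet figure has lost or never had its sign. That calls for a check against the source. But four greater-than signs in one row next to legible less-than signs, and the per-µL unit printed four times, do not resemble that damage.

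**Conclusion.** The point holds for two sub-tables of management guidance. The 8.4 Grade 3-4 row contradicts Grade 2 on all four measures and cannot be reached by worsening from Grade 2. The 8.6 cut-offs are 1,000-fold below the section 10.1 unit and at odds with the 20,000 in 8.4; a count of 20,000/µL matches no row, so that table prompts no hold or treatment. The factor of 1,000 is exactly the conversion between the two units, which suggests a unit slip, but the documents cannot confirm it.

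It would go too far to infer that the trial's results or its safety monitoring are compromised. The definition of unacceptable toxicity in section 23 names no hematologic grade. A hematologic event could count there by delaying surgery beyond the stated interval, but not through a Table A8 grade. MPR is read from the resected specimen. Neither depends directly on these rows.

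The conclusion assumes that the signs and units appear in the source document as they do here, and that the 8.4 counts are per µL. The marrow contradiction needs only the first assumption.

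**What to change.** The sponsor should:

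- check the 8.4 Grade 1 and Grade 3-4 rows and all of 8.6 against the guideline that Appendix 1 reproduces;
- reconcile direction and units in 8.4 and 8.6 with each other and with section 10.1, printing the unit beside every count;
- reconcile these rows with the CTCAE v5.0 grading named in 14.7.2, so that it is clear which grade drives the management step.

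This review proposes no threshold and does not choose which rule governs. The cost is an appendix correction and a notice to the treating team. Design, sample size and analysis are unchanged.
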